3.2.1 Visit 1: Pre-Operative Visit

Information will be collected on the study population prior to device implantation. Demographic factors including age, gender and primary diagnosis will be obtained.

Procedures to be completed at the pre-operative visit:

- confirm informed consent and inclusion/exclusion criteria are met
- assign a subject ID
- collect data per case report form (CRF) completion guidelines, including demographic data, mHHS, Charnley Classification, ASA score (American Society of Anesthesiologists), and prior hip surgery.
- Perform all study procedures per study schematic

CONFIDENTIAL AND PROPRIETARY

This document contains information that is confidential and proprietary to Smith & Nephew PLC and Smith & Nephew, Inc. and is intended for use only by Smith+Nephew and its manufacturer. It shall not be reproduced or copied in whole or in part, nor shall the contents be disclosed by any means without prior written permission from Smith+Nephew, nor shall anyone make any use of it that is contrary to the expressed or implied wishes of Smith+Nephew.

Statistical Analysis Plan

Post-Approval Study of the R3™ Biolox® delta Ceramic Acetabular System – United States

Number: 16-4565-10
ST: 1176
Version: 5.2, 19-JAN-2024
Page: 10 of 22

3.2.2 Visit 2: Intraoperative to Hospital Discharge

Information on the operative procedure for each subject including surgical approach, component size and device identifier, surgical time, and intraoperative blood loss will be obtained. Additionally, length of hospital stay and discharge to home or any other institution will be recorded. Any adverse events (complications) occurring from the time of study device implant and prior to discharge will be collected and recorded on the appropriate CRF.

Patients will have radiographs taken after implantation (before discharge from the hospital) to establish a baseline. All study radiographs (Anteroposterior (AP) pelvis, AP hip, and lateral hip) should be acquired according to the Image Acquisition Protocol and will be transmitted to the central imaging vendor for independent review.

3.2.3 Visit 3: Postoperative

Postoperative follow-up visits will occur at 3 months (+/- 2 weeks), 1 year (+/- 2 months), 2 years (+/- 2 months) and 3 years (+/- 2 months) postoperative. Subjects will be evaluated using the modified Harris Hip Score (mHHS) that was used in the original European post-market surveillance study. The mHHS includes a modification to the "Distance Walked" section of the Harris Hip Score to add distances to the choices available, such as indicating the number of blocks as a defined distance since the term "blocks" is not commonly used as a measurement of distance in Europe.

AP and lateral radiographs will be taken at these postoperative visits. All study radiographs (AP pelvis, AP hip, lateral hip) should be acquired according to the Image Acquisition Protocol. X-rays will be transmitted to the central imaging vendor for independent review. Radiographs will be evaluated by an independent evaluator according to the Smith & Nephew Radiographic Evaluation Protocol.

Procedures to be completed at the postoperative visits:

- perform study procedures per study schematic
- perform required X-rays (see Appendix II for subject positioning details)
- transmit X-rays to the central imaging vendor
- obtain and record any adverse events (AEs) occurring from the time of study device implantation
- collect data per CRF completion guidelines

CONFIDENTIAL AND PROPRIETARY

This document contains information that is confidential and proprietary to Smith & Nephew PLC and Smith & Nephew, Inc. and is intended for use only by Smith+Nephew and its manufacturer. It shall not be reproduced or copied in whole or in part, nor shall the contents be disclosed by any means without prior written permission from Smith+Nephew, nor shall anyone make any use of it that is contrary to the expressed or implied wishes of Smith+Nephew.

Statistical Analysis Plan

Post-Approval Study of the R3™ Biolox® delta Ceramic Acetabular System – United States

Number: 16-4565-10
ST: 1176
Version: 5.2, 19-JAN-2024
Page: 11 of 22

3.2.4 Telephone Follow-Up

If subjects are unable to return for follow-up visits to the Investigator's office, they may be contacted by telephone to assess their status. Subjects will be asked whether the device is in place or has been revised and asked whether any adverse events related to the study hip device have occurred since the last visit.

In addition, the patient portion of mHHS (all data except for Range of Motion (ROM), Trendelenburg and Leg Length Difference) will be collected during this Telephone Follow-Up Assessment^{1,2}. Note that if the subject later returns for a follow-up visit to the Investigator's office during the same interval as a telephone follow-up visit, the complete mHHS will be collected and included in the analyses in lieu of the patient portion.

The proposal to collect the patient portion of the mHHS data by telephone interview, and to use these data in lieu of the full mHHS when necessary, is justified based on the clinical study that has been published in the Journal of Telemedicine and Telecare in 2005² which confirms that there is overall no statistical difference between in-office complete mHHS and telephone patient portion mHHS assessments. Note that 'mHHS' in this study refers to a modification in how the "distance walked" question is asked, to make it more relevant for the European study population. However, in the article², 'mHSS' refers to the patient portion of the HHS without ROM, Trendelenburg and Leg Length Difference, as these cannot be collected remotely. Removal of the ROM and deformity components gives a maximum score of 91, which is multiplied by a factor of 1.1 in order to derive a total score out of 100. The published study showed that the differences between the complete HHS and the patient portion of the HHS are not statistically significant or clinically relevant, and thus the patient portion can be used for routine follow-up assessment of patients who have undergone total hip replacement².

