6.5. Telephone Follow-Up

If subjects are unable to return for follow-up visits to the Investigator's office they may be contacted by telephone to assess their status. Subjects will be asked whether the device is in place or has been revised, and asked whether any adverse events have occurred since the last visit.

Smith & Nephew - Advanced Surgical Devices Division

Post-Approval Study of the R3™ Biolox® delta Ceramic Acetabular System – United States	Number: 16-4565-10
	Version 6.0
	Page: 16 of 28

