8.2. Safety: Investigator's Responsibilities

Investigators shall record adverse events and observed device deficiencies, together with an assessment of seriousness, severity, and device/procedure relatedness, in the subject's source data. Following, Investigators are responsible for documenting AEs and device deficiencies on the appropriate CRF and submitting them to the Sponsor according to the timelines described here below.

At each contact with the subject, the Investigator must seek information on AEs by specific questioning and, as appropriate, by assessment of the subject. AEs must be recorded in standard English medical terminology.

Unresolved AEs should be followed by the Investigator until the events are resolved, the subject is lost to follow-up or through to the end of the study, whichever timing occurs first. Unresolved AEs at the end of the subject's participation will be monitored by the Investigator as part of the site's normal standard of care.

The Investigator will categorize AEs as mild, moderate or severe based on the following definitions:

- Mild: the subject is aware of the sign or symptom, but finds it easily tolerated. The event is of little concern to the subject and/or little clinical significance. The event is not expected to have any effect on the subject's overall health or wellbeing.
- Moderate: the subject has discomfort enough to cause interference with or change in usual activities. The event is of some concern to the subject's health or wellbeing and may require medical intervention and/or close follow-up.
- Severe: the adverse event interferes considerably with the subject's usual activities. The event is of definite concern to the subject and/or poses substantial risk to the subject's health or wellbeing. The event is likely to require medical intervention and/or close follow-up and may be incapacitating or life threatening. Hospitalization and treatment may be required.

The Investigator is responsible for describing the relationship of the AE to the study device/procedure based on the following definitions:

- Unrelated: the event is clearly not related to the study device or procedure
- Possible: the event may or may not be related to the study device or procedure. A relationship cannot be ruled out.
- Definite: the event is clearly related to the study device or procedure.

8.3. Timelines for Submission of Safety Information:

The timelines begin when the Investigator becomes aware of the event.

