7.13 Analysis of Safety Endpoint(s)

The number of AEs, SAEs, USADEs, Reoperation and Revisions, and the number and the percentage of patients experiencing AEs, SAEs, USADEs will be presented for the enrolled set.

The number of AEs and the number and the percentage of patients with at least one AE will be presented for AEs and SAEs.

The number and the percentage of patients with at least one AE will be presented by severity, seriousness, device relatedness and procedure relatedness.

Adverse event definitions are shown below and are as per the study protocol.

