7.13.1 Adverse Event (AE)

An AE is any untoward medical occurrence, unintended disease or injury, or untoward clinical signs (including abnormal laboratory findings) in subjects, users, or other persons, whether or not related to the study medical device.

This definition includes but is not limited to:

- events related to the study device
- events related to the procedures involved

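### SAP 3.2.4 narrows the telephone adverse-event question to device-related events, contradicting protocol 6.5 and 8.2; if calls used that wording, the all-AE and SAE rates could be too low

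*SAP*

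**What the plan says.** On the telephone contact itself, the two documents differ by one phrase:

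- Protocol 6.5: subjects are "asked whether any adverse events have occurred since the last visit".
- SAP 3.2.4: subjects are "asked whether any adverse events related to the study hip device have occurred since the last visit".

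Other text bears on which version is meant:

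- Protocol 8.2: "At each contact with the subject, the Investigator must seek information on AEs by specific questioning". The same section makes relatedness an assessment by the investigator.
- SAP 7.13.1, like protocol 8.1, defines an adverse event "whether or not related to the study medical device".
- SAP 3.2.3 asks staff at postoperative visits to "obtain and record any adverse events (AEs) occurring from the time of study device implantation".
- The SAP 3.2 schedule marks adverse-event assessment at every postoperative visit, and its telephone footnote refers the reader to protocol 6.5.
- SAP 5.4 sets no relatedness limit on the events to be recorded.

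On use of the data, SAP 7.3 takes telephone data into the analyses where it can when an office visit is missed. For all enrolled subjects together, SAP 7.13 then plans as follows: "The number of AEs and the number and the percentage of patients with at least one AE will be presented for AEs and SAEs", with a breakdown "by severity, seriousness, device relatedness and procedure relatedness". It makes no distinction by visit mode. SAP 3.2.4 gives no reason for the narrower question. SAP 7.15 declares no departure from the protocol, although that section covers analysis methods only.

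**The concern.** A question limited to device-related events asks the subject to judge relatedness before anything is recorded. Events the subject thinks have nothing to do with the hip may never reach the investigator, who is the person assigned to judge relatedness. Events related only to the procedure also fall outside the question, although SAP 7.13 tabulates them. Protocol 10.4 lists complications such as deep venous thrombosis, embolism and myocardial infarction, which a subject might not connect with the implant.

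Safety is part of the study objective, and telephone contact was expected to be common enough to plan for. Enrollment ran from February 2018 to October 2019, so the 3-year visits with their 2-month windows fall between about December 2020 and December 2022. SAP 7.6 expects COVID-19 visit restrictions and relies on the telephone survey at 3 years. If ascertainment differed between calls and office visits, a single pooled AE table would mix two different measurements.

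**Working it through.** The documents give no figure on this point, and the sample size (146, or 183 after allowance for loss) plays no part in it. The check is a comparison of text, followed by an illustration of size on assumed inputs.

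**1. Scope of the question, by source**

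| Source | Events covered |
|---|---|
| Protocol 6.5, telephone | Any adverse event |
| Protocol 8.2, every contact | Adverse events, no relatedness limit |
| SAP 3.2 footnote, telephone | As protocol 6.5 |
| SAP 3.2.3, postoperative visits | Any adverse event since implantation |
| SAP 5.4 and 7.13.1 | Related or not |
| SAP 3.2.4, telephone | Hip-device-related only |

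The last row stands alone. It conflicts with two protocol sections and with the rest of the SAP.

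**2. What the outputs need.** SAP 7.13 counts "The number of AEs, SAEs, USADEs, Reoperation and Revisions" without restriction and splits AEs by device and procedure relatedness. Those tables are consistent across contacts only if every contact used the unrestricted question.

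**3. Where a missed event stays missed.** Postoperative visits collect events back to implantation, so a later office visit can recover what a call missed. The 24-hour SAE reporting rule in protocol 8.3 starts when the investigator becomes aware, so it does not help with an event nobody mentioned. SAP 7.3 and 7.6 allow late returns after the 3-year window, but they name hip scores and radiographs, not adverse events. Permanent loss is therefore most plausible for a final 3-year call with no later office visit.

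**4. Size, on assumed inputs.** Let

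- f = share of subjects contacted by telephone in an interval,
- u = share of adverse events the subject would not attribute to the device,
- r = share of those events recovered by another route.

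None of the three is in the documents. With equal event rates by visit mode, and if the narrower question was asked literally:

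relative loss in the interval's AE count = f × u × (1 − r)

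With no recovery (r = 0):

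- f = 0.05, u = 0.5: 0.05 × 0.5 = 2.5%
- f = 0.20, u = 0.7: 0.20 × 0.7 = 14%
- f = 0.40, u = 0.9: 0.40 × 0.9 = 36%

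Recovery shrinks these in proportion. With r = 0.5 the middle case is 14% × 0.5 = 7%, and with full recovery the loss is zero.

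Suppose also that the subject's attribution agrees with the investigator's. The true device-related share of events is then 1 − u, and the observed share with no recovery is (1 − u) / (1 − f × u):

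- f = 0.05, u = 0.5: 0.50 / 0.975 = 51%, against 50%
- f = 0.20, u = 0.7: 0.30 / 0.86 = 35%, against 30%
- f = 0.40, u = 0.9: 0.10 / 0.64 = 16%, against 10%

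These figures concern event counts in one interval. The percentage of patients with at least one AE cannot be derived from them, because a patient who loses one event may still be counted for another.

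**5. Primary endpoint.** In the same call SAP 3.2.4 asks separately whether the device is in place or has been revised. The hip score and radiographic components do not use the adverse-event question. The endpoint is untouched by this wording.

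**The case against.** The strongest reply is that the phrase had no effect. Sites work from the protocol, and protocol 6.5 and 8.2 are unambiguous. The SAP itself sends telephone follow-up back to protocol 6.5. SAP 5.2 is dated 19 January 2024, while the protocol synopsis has data collection complete by May 2023, so this version cannot have directed any call. Events that are recorded are still assessed for relatedness under protocol 8.2 and SAP 7.13.8, and later office visits can pick up what a call missed.

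Most of this stands, and it is why the under-count can only be stated conditionally. It does not remove the contradiction. The version history does not say when the phrase entered the SAP, and the text of the telephone form is not in the documents supplied. Until the form is checked, it is unknown which question was asked.

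A reader might also infer that the wording biases the comparison with the European cohort in the device's favour. The documents do not support that. They do not say how the European study asked about adverse events, SAP 7.13 is descriptive, and no formal safety comparison is planned. The directions are also mixed: total AE and SAE rates would fall, but the device-related share would rise.

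**Conclusion.** The inconsistency is certain: SAP 3.2.4 is wrong as written against protocol 6.5 and 8.2 and against the SAP's own definition and footnote. It is a SAP-protocol inconsistency. Nothing indicates a deliberate design choice.

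The consequence is conditional. If calls used the narrower question, and if missed events were not recovered later, the all-AE and SAE rates in SAP 7.13 would be too low and the device-related share of events too high. The effect would fall mainly on final 3-year calls with no later office visit. It would be tempting to conclude that the reported rates are under-counted, but nothing in the documents shows that the narrower question was ever asked.

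The size cannot be computed from the documents. The 2.5% to 36% range above only shows how the loss depends on assumed inputs; it is not an estimate, and it assumes equal event rates by visit mode and no recovery. The primary endpoint is not affected.

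**What to change.** 1. Reconcile SAP 3.2.4 with protocol 6.5 and 8.2, so that the telephone question is stated once and consistently.
2. Check which question the telephone form carried, and state it in SAP 7.13.
3. Only if the narrower question was used: flag those contacts, report all-AE, SAE and unrelated-AE rates both overall and for intervals with full questioning, and state the limitation beside the tables.

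Because data collection is over, rewording recovers no events. It corrects the record and tells the reader how to interpret the safety tables. The cost is one sentence in the SAP, one look at the form, and possibly one additional safety table.

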4 STUDY OBJECTIVES

The study objective is to confirm that the safety and effectiveness of the R3 Biolox delta Ceramic Acetabular System in the US population is consistent with the effectiveness and safety profile shown in the European study (PMA cohort).

¹ Range of Motion, Trendelenburg and Leg Length Difference must be determined in person by clinically trained site staff to collect these data points in a reliable and clinically accurate manner.

² Sharma, et al. "Use of telephone interviews to follow up patients after total hip replacement." Journal of Telemedicine and Telecare Volume 11 Number 4 2005

CONFIDENTIAL AND PROPRIETARY

This document contains information that is confidential and proprietary to Smith & Nephew PLC and Smith & Nephew, Inc. and is intended for use only by Smith+Nephew and its manufacturer. It shall not be reproduced or copied in whole or in part, nor shall the contents be disclosed by any means without prior written permission from Smith+Nephew, nor shall anyone make any use of it that is contrary to the expressed or implied wishes of Smith+Nephew.

Statistical Analysis Plan

Post-Approval Study of the R3™ Biolox® delta Ceramic Acetabular System – United States

Number: 16-4565-10
ST: 1176
Version: 5.2, 19-JAN-2024
Page: 12 of 22

5 STUDY ENDPOINTS

5.1 Primary Endpoint(s)

The primary endpoint is overall study success at 3 years postoperative. Success is defined the same way it was in the PMA cohort, to allow comparison. The primary endpoint will be analyzed using the exact binomial test. Overall success is defined as:

- No component revision,
- Modified Harris Hip Score (mHHS) of at least 80 points, and
- No radiographic failure, defined as:

No radiolucencies greater than 2 mm in 50% or more in any of the cup or stem zones, no femoral or acetabular subsidence greater than or equal to 5 mm from baseline, and no acetabular cup inclination changes greater than 4 degrees from baseline when accompanied by "Mild", "Moderate", "Marked" or "Disabled" mHHS pain score.

In the event that the need for remote visits due to COVID-19 significantly impacts the primary endpoint, the following additional analyses will be performed to allow inclusion of as many study subjects as possible in the analysis:

- (1) An alternative analysis in which overall success will consist of components that can be remotely collected via telephone, and will be defined as:
 - No component revision,
 - Patient portion of the Modified Harris Hip Score (mHHS), as described in Section 3.2.4**Error! Reference source not found.**, of at least 80 points.
- (2) An alternative analysis that allows for post-three-year data to be used in place of missing or incomplete three-year visits ("rollback").

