7.3 Handling of Missing, Incomplete and Repeat Data

When data are being summarized, only the non-missing values will be evaluated for computing summary statistics.

In general, partial dates will be imputed as follows:

- if only the day is missing, the first day of the month will be assumed;
- if the day and the month are missing, January 1st will be assumed;
- if a date is completely missing or unknown and the visit is not indicated on the CRF, the data will not be included in a specific time window for analysis. Note that all AEs will be included regardless of whether the date is missing or incomplete.

When subjects do not attend an in-office study visit and a telephone visit is conducted instead, the data from telephone visit will be used for analyses wherever possible.

When the patient misses the final (3 year) visit but is able to return the office at a later date, the additional mHHS and radiographic data that were not collected during the telephone visit will be collected and used for the final analyses at 3 years.

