Due to subject visit restrictions associated with COVID-19 pandemic, it is expected that Protocol Deviations will occur that may affect the subject accountability rates. In particular, radiographic data and data that can only be collected at the office follow up are likely to be missing or out of window. However, the telephone survey will ensure that most of the key information needed for the primary analysis at the 3-year follow-up visit is collected. Additionally, every effort will be made to gather radiographic data and the complete HHS at a later time when an in-person visit was not completed within the 3-year window.

To present a thorough assessment of hip accountability, the following information will be included in the annual reports and final study report:

- (1) The typical accountability table that has been presented in each annual report will be presented, using the same rules for inclusion in each category (i.e. Actual^A, Actual^{Awithinwindow}, Actual^B, Actual^{Mod. B}).

CONFIDENTIAL AND PROPRIETARY

This document contains information that is confidential and proprietary to Smith & Nephew PLC and Smith & Nephew, Inc. and is intended for use only by Smith+Nephew and its manufacturer. It shall not be reproduced or copied in whole or in part, nor shall the contents be disclosed by any means without prior written permission from Smith+Nephew, nor shall anyone make any use of it that is contrary to the expressed or implied wishes of Smith+Nephew.

Statistical Analysis Plan

Post-Approval Study of the R3™ Biolox® delta Ceramic Acetabular System – United States

Number: 16-4565-10
ST: 1176
Version: 5.2, 19-JAN-2024
Page: 17 of 22

- (2) Final 3-year accountability, which will include telephone visit data (or full HHS if available) plus out-of-window radiographic data as allowable for "complete data" (Actual^Awithinwindow, and Actual^A), and telephone visit data alone as allowable for other accountability categories including Actual^B and Actual^{Mod. B}.
- (3) A listing of deviations and missed/out of window visits that result from the COVID-19 pandemic.

Screening failures and patients discontinued from the study prematurely will be presented with a breakdown of the reasons for discontinuation as reported in the CRF.

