7.10 Analysis of Primary Endpoint(s)

The primary endpoint is overall study success at 3 years postoperative. Success is defined the same way it was in the PMA cohort, to allow comparison. Overall success is defined as:

- No component revision,
- Modified Harris Hip Score (mHHS) of at least 80 points, and
- No radiographic failure, defined as:

No radiolucencies greater than 2 mm in 50% or more in any of the cup or stem zones, no femoral or acetabular subsidence greater than or equal to 5 mm from baseline, and no acetabular cup inclination changes greater than 4 degrees from baseline when accompanied by "Mild", "Moderate", "Marked" or "Disabled" mHHS pain score.

All subjects in the enrolled population with evaluable data at 3 years postoperative will be considered for analysis. Subjects lost to follow up due to revision at any point up to the end of the three-year visit window will be considered as failures.

A one-sided analysis using the exact binomial model will be used to analyze success rate against the success rate of the PMA cohort of 86.4%, with 8% margin (as per Sample Size Section 6.1).

As mentioned in Section 7.14 additional analyses will be performed to accommodate inclusion of as many study subjects as possible in the analysis.

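### Does the telephone-only version of overall success in SAP 5.1 need its own benchmark, or a ban on using 86.4% minus 8 points?

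*SAP*

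**What the plan says.** SAP 5.1 defines overall success at 3 years by three components: no component revision, mHHS of at least 80, and no radiographic failure. It gives the reason for keeping that definition: "Success is defined the same way it was in the PMA cohort, to allow comparison". SAP 6.1 ties the 86.4% PMA rate to that same definition. SAP 7.10 restates the three components and then tests the success rate "against the success rate of the PMA cohort of 86.4%, with 8% margin", using a one-sided exact binomial test.

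SAP 5.1 also lists two additional analyses, to be run only if COVID-19 remote visits significantly affect the primary endpoint. In alternative (1), "overall success will consist of components that can be remotely collected via telephone", namely no revision and a patient-portion mHHS of at least 80. Alternative (2) lets data collected after three years stand in for missing or incomplete three-year visits; it removes no component. No reference rate, margin or test is stated for (1).

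SAP 7.10 closes with a pointer: "As mentioned in Section 7.14 additional analyses will be performed to accommodate inclusion of as many study subjects as possible in the analysis". SAP 7.14 holds race summaries, a t-test of mHHS from in-person against telephone visits, and a Fisher's exact test of cup inclination change against pain. Neither alternative (1) nor (2) appears there.

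On missed visits, SAP 7.3 says that "the data from telephone visit will be used for analyses wherever possible". For subjects who miss the 3-year visit but come back later, the outstanding mHHS and radiographic data "will be collected and used for the final analyses at 3 years". SAP 7.6 adds that "every effort will be made to gather radiographic data and the complete HHS at a later time".

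**The concern.** Alternative (1) keeps the name overall success and sits under the primary-endpoint heading, but a subject whose only failure is radiographic now counts as a success. With the same subjects and the same mHHS classification, dropping a failure criterion can raise the success rate or leave it unchanged; it cannot lower it.

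The SAP contains just one success-rate test, the one in 7.10, and the sentence after it introduces the additional analyses. SAP 7.6 says the telephone survey will ensure that "most of the key information needed for the primary analysis at the 3-year follow-up visit is collected". A reader could conclude that the two-component rate should also be held against 78.4%. That would not compare like with like, and a pass would not show consistency with the European three-component rate, which is the objective of the study. The faulty pointer to 7.14 leaves the question open.

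**Working it through.** **Inputs.** PMA rate 0.864, margin 0.08, one-sided alpha 5%, power 80%, 146 evaluable, 20% loss, 183 in total (SAP 6.1). Telephone score: maximum 91, multiplied by 1.1 (SAP 3.2.4). The share failing on radiographs only, r, is not in the documents; 0 to 5 points is assumed.

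**1. The plan's own figures.** The null boundary is 0.864 − 0.08 = 0.784. The pass mark c is the smallest count with P(X ≥ c | n = 146, p = 0.784) ≤ 0.05.
- c = 122 gives 0.0753; c = 123 gives 0.0492. The pass mark is 123.
- Power is P(X ≥ 123 | 146, 0.864) = 0.8125.
- 146 / 0.80 = 182.5, rounded up to 183.

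Both 146 and 183 reproduce.

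**2. What would follow if 78.4% were carried over.** Let S3 be the three-component rate and S2 the two-component rate. If the patient-portion mHHS classifies subjects as the full score does, S2 = S3 + r. With the same r in the PMA cohort, the matching reference would be 0.864 + r, so a fixed goal of 0.784 implies a margin of (0.864 + r) − 0.784 = 8 + r points. With S3 = 0.784, the chance of passing is P(X ≥ c | n, 0.784 + r):

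| r (assumed) | n = 146, c = 123 | n = 183, c = 153 |
|---|---|---|
| 0 | 4.9% | 4.9% |
| 1 point | 8.6% | 9.2% |
| 2 points | 14.2% | 15.9% |
| 3 points | 22.1% | 25.4% |
| 5 points | 44.5% | 51.9% |

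**3. How far these figures can be trusted.** Total failure in the PMA cohort was 100 − 86.4 = 13.6%. If the US rate is similar, r = 5 points would make radiograph-only failures 5 / 13.6 = 37% of all failures, and r = 1 point would make them 1 / 13.6 = 7%. The documents give no basis for choosing between these. r is also smaller than total radiographic failure, because cup inclination change counts only when there is pain, and pain may go with a low mHHS.

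The rescaling can push either way. A raw score of 73 gives 73 × 1.1 = 80.3 and passes by telephone, but the full score reaches 80 only with 7 of the remaining 100 − 91 = 9 points. Raw 72 (79.2) and raw 71 (78.1) fail by telephone, but would pass in full with 8 or 9 of those points. If r and the scoring effect together came to −1 point, the chance of passing at n = 146 would be 2.7%, below the nominal 5%.

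**4. What the SAP directs.** The benchmark is stated with the three-component definition in both 6.1 and 7.10, and 5.1 says why the definitions must match. Alternative (1) is called additional and alternative, is conditional, and is nowhere given a hypothesis. The 7.6 remark about telephone data belongs to subject accountability. It follows a warning that radiographs are likely to be missing or out of window, and comes just before the commitment to collect them later. It therefore treats radiographs as still needed.

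**5. How the result would read without a test.** SAP 7.1 plans 95% intervals for the primary endpoint, and the same summary serves (1). A count of 123 out of 146 would be 84.2%, exact 95% interval 77.3% to 89.7%.

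**The case for a change.** The best case for a change is that it costs little. Two sentences would declare (1) supportive and rule out a test against 78.4%. SAP 5.1 names the exact binomial test for the primary endpoint and then lists (1) under the same heading, nothing expressly forbids the carry-over, and the trigger for running (1) has no numerical threshold. If (1) were reported as meeting 78.4%, the error would favour the device.

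Most of this is factually right. The SAP is silent on the status of (1), the direction of the bias from dropping radiographs is clear, and the calculations hold. What does not follow is that the plan produces a wrong answer. Harm needs a chain of events: COVID-19 significantly affects the endpoint, (1) is run, someone applies 78.4% to it against the SAP's own reason for a common definition, r is material, and the result is then read as showing consistency. The SAP prescribes only that (1) be run if the trigger is met.

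A stronger remedy would be to re-score the PMA cohort on the same two components. With equal r in both cohorts, the pass mark at n = 146 would be 125, 126, 127 or 130 for r = 1, 2, 3 or 5 points, with power of 78%, 82%, 86% or 88%. It needs item-level PMA data, which the documents do not show to be held.

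The pointer in 7.10 is incomplete rather than empty. SAP 7.14 does contain a COVID-related additional analysis, the t-test, and alternatives (1) and (2) are found in 5.1. A reader with the SAP in hand finds both.

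**Conclusion.** No change follows. The observation is accurate: alternative (1) drops the radiographic criterion and has no stated comparator, and 78.4% would be the wrong one. But the gap is missing detail in a conditional, supportive analysis, and the SAP's wording already leads an analyst to the sensible reading: the benchmark stays with the three-component endpoint, and (1) is an estimate with an interval. The primary test, its size of 4.9% and its power of 81% at 146 subjects are unaffected. Late radiographs are to be collected and used, and alternative (2) removes no component. The incomplete cross-reference in 7.10 is clerical.

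The 8.6% to 44.5% range for r of 1 to 5 points is illustrative only. It assumes that 78.4% is applied to (1), that the true three-component rate sits exactly on the null boundary, that n is 146, and that telephone and full mHHS scores classify subjects alike. The view would change if a report presented alternative (1) as having met 78.4%. That would be a fault of the report, since the plan does not call for it.
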